2 STUDY OBJECTIVES AND DESIGN

2.1 Study Objectives

The objectives of this study are as follows:

Primary Endpoint (14 patients with measurable disease)

To estimate best overall response rate by RECIST 1.1¹³ in patients with measurable disease determined by a. CT or b. MRI

Secondary Endpoints (All patients)

- 1. To estimate progression-free survival at 1-year
- 2. To correlate blood pressure control and change/discontinuation of antihypertensive medications with tumor responses
- 3. To correlate symptomatology evaluation by the MD Anderson symptom Inventory (MDASI) with tumor responses
- 4. To correlate plasma metanephrines and chromogranin A with tumor responses
- 5. To correlate plasma C-reactive protein and interleukin-6 with symptoms and tumor responses
- 6. Toxicity assessment by the Common Terminology Criteria for Adverse Events (CTCAE)
- 7. To correlate both c-MET expression by IHC as well as MET amplification by FISH in archived samples and correlate these biomarkers with overall prognosis and responsiveness to cabozantinib.

Exploratory Endpoints (For patients with only bone metastases)

- 1. Best overall response rate in patients with bone metastases only (8 patients) as determined by FDG-PET/CT
- 2. FDG-PET/CT SUV_{max}, advanced volumetric measures including SUV_{peak}, metabolic tumor volume (MTV), and total lesion glycolysis (TLG)
- 3. Time to skeletal related events
- 4. Incidence of skeletal related events at 4 months and one year
- 5. Markers of bone turnover (bone specific alkaline phosphatase and CTx)

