protein). CTx will be done, if patient has bone metastases, at screening and every 8 weeks during the first 52 weeks, then every 12 weeks.

If the subject is unable to have a study assessment taken within the defined time window due to an event outside of his or her control (eg, clinic closure, personal emergency, inclement weather, vacation), the assessment should be performed as close as possible to the required schedule.

Regular tumor assessments should be performed in accordance to the guidelines in Section 5.5 to determine if PD is present.

The Treatment Period ends when a subject receives his or her last dose of study treatment; the subject then enters the Post-Treatment Period.

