5.3 Post-Treatment Period

Subjects will return to the study site 30 to 37 days after their last dose of cabozantinib to complete end-of-study assessments.

Laboratory and physical examinations will be performed. Remaining study treatment will be returned by the subject, and treatment compliance will be documented. Additional follow-up will occur for subjects with AEs related to study treatment that are ongoing at the time of this visit, and for subjects with SAEs related to study treatment that occur after the time of this visit.

²Every 4 weeks through Week 24, then every 8 weeks through 52 weeks, then every 12 weeks.

³All sites of known disease must be assessed. To occur every 8 weeks during the first 52 weeks, then every 12 weeks.

⁴Patients with both bone and visceral metastases.

⁵Patients with bone metastases only. This is the **only tumor assessment for patients with bone metastases only**.

⁶ No additional measurements of plasma metanephrines are needed in patients with normal plasma metanephrines at baseline (Non-functioning PH or PG).

⁷ Starting after week 24, nursing phone calls to take place every 8 weeks, at the 4 week period between visits (+/- 5 days). After week 52, phone calls to take place every 12 weeks, at the 6 week period between visits (+/- 5 days). Phone calls will comprise AE and concomitant medication assessments.

⁸ MDASI questionnaires will be completed if the patient can be contacted and is willing and able to complete the questionnaire. While patients are encouraged to complete questionnaires at all scheduled time points, patients may refuse to complete a questionnaire at any time.

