5.5 Tumor Measurements

Tumor response should be assessed at a frequency of 8 weeks for the first 52 weeks (and then every 12 weeks after that) by CT/MRI and based on RECIST 1.1. In patients with bone metastases, an FDG-PET scan will be obtained every 8 weeks for the first 52 weeks (and then every 12 weeks after that). Subjects continuing to show benefit (complete response [CR], partial response [PR], or stable disease [SD]) may continue on study. Subjects with PD should have their treatment discontinued (unless the investigator, with approval of the Medical Monitor, judges the patient is deriving clinical benefit), and they should enter the post-treatment phase of the study. The same method for tumor assessment should be employed at every assessment.

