7 STATISTICAL CONSIDERATIONS

This Phase II study's primary objective is to estimate the best overall response rate in patients with measurable disease. Response will include RECIST 1.1 CR, PR, and SD. With 14 patients, the 95% confidence interval for a 45% response rate would be (18.9, 71.1%). For the exploratory objective in the small group of patients with bone metastases, the 95% confidence interval for a 45% response rate with 8 patients would be (10.5, 79.5%). We do not include a formal statistical monitoring rule for toxicity given the established safety profile of this drug.

Continuous variables will be summarized using descriptive statistics such as mean, standard deviation, median and range. Categorical variables will be tabulated by frequencies and the corresponding percentages. Response rates and their 95% confidence intervals will be estimated. Kaplan Meier survival curves will be used to estimate survival outcomes. Cox proportional hazards regression analysis may be used to assess the association between survival and covariates of interest. The Fisher's exact test or logistic regression analysis will be used for any binary outcomes. T-tests or Wilcoxon rank sum tests will be used to compare continuous variables. Longitudinal models may be explored to study change over time.

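### No tumor imaging is scheduled after the last dose and routine follow-up ends 30 to 37 days later, so patients who stop without progression have truncated 1-year PFS data

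*Combined protocol and SAP*

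**What the plan says.** Section 2.1 gives the first secondary endpoint, for all patients, as "To estimate progression-free survival at 1-year". Secondary endpoint 7 will measure MET and "correlate these biomarkers with overall prognosis and responsiveness to cabozantinib". Section 7 adds that "Kaplan Meier survival curves will be used to estimate survival outcomes", with no definition of a PFS event and no censoring rule.

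Section 5.2 closes treatment at the last dose: "The Treatment Period ends when a subject receives his or her last dose of study treatment; the subject then enters the Post-Treatment Period". In Table 5-1 the tumor assessment, bone scan and FDG-PET rows are marked at screening and during treatment and are blank in the post-treatment column.

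Section 5.3 then says "Subjects will return to the study site 30 to 37 days after their last dose of cabozantinib to complete end-of-study assessments". It continues "Laboratory and physical examinations will be performed", and "Additional follow-up will occur for subjects with AEs related to study treatment that are ongoing at the time of this visit", extended to drug-related serious adverse events (SAEs) that occur after the visit. Section 6.1.2 counts death as an SAE and captures SAEs to 30 days after the last dose, and later ones only if related to treatment.

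Two other places are less clear. Section 2.2.1 says the Post-Treatment Period includes follow-up contacts and refers to Section 5.3 for them, but Section 5.3 describes no contacts for disease status or survival. Section 5.5 says "Tumor response should be assessed at a frequency of 8 weeks for the first 52 weeks" and every 12 weeks thereafter, without saying whether this continues off drug.

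**The concern.** Section 2.5 lists several ways to leave treatment without progression: an adverse event or intercurrent illness, failure to tolerate the minimum dose, noncompliance, need for a prohibited anticancer therapy, withdrawal of consent, or the investigator's judgment. For patients who leave this way but stay in the study, no later progression is scheduled to be observed, and an unrelated death after 30 days is not captured. With no PFS rule in Section 7, the natural Kaplan-Meier handling is to censor them near the last on-drug scan.

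That handling is harmless only if, after stopping, these patients progress at the rate of those who stay on drug. If they progress faster, the curve describes PFS as though everyone had remained on treatment, and the 1-year figure is too high. Whatever MET is found to correlate with under objective 7 would be limited to the treatment period and about a month beyond it. Data not collected cannot be recovered at analysis.

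**Working it through.** **The plan's own precision figures.** The plan gives intervals only for response rates. The Wald formula p ± 1.96·√(p(1−p)/n) at p = 0.45 gives 18.9 to 71.1% for n = 14 and 10.5 to 79.5% for n = 8, matching Section 7. They do not depend on post-treatment follow-up. The plan states no precision for 1-year PFS. The same formula at p = 0.50 and n = 22, with everyone followed, gives a half-width of 1.96·√(0.25/22) = 20.9 points.

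**Bounds with no hazard assumption.** If j of 22 patients stop unprogressed before 12 months and their later status is unknown, the simple 1-year proportion is unresolved by j/22: 9.1 points for 2 patients, 18.2 for 4, 27.3 for 6.

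**Bias under a simple model.** The documents give no stopping rate, off-drug hazard or expected PFS for this trial, so these are assumptions:
- on-drug hazard λ constant, with 12λ = ln 2, so the Kaplan-Meier estimate tends to exp(−12λ) = 50%;
- stopping hazard μ constant, with 1 − exp(−12μ) = 10, 20 or 30%;
- hazard kλ after stopping, with k = 1, 2 or 3.57. The last is 1/0.28, from the drug-versus-placebo hazard ratio in medullary thyroid cancer (Section 1.1.1.5);
- no event after stopping is recorded. This slightly overstates the loss, because deaths to 30 days are captured.

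At these rates about 1.6 patients (10%) to 4.9 patients (30%) of 22 would stop unprogressed within the year: 22·[μ/(λ+μ)]·[1 − exp(−12(λ+μ))].

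True PFS(12) = exp(−12(λ+μ)) + ∫₀¹² μ·exp(−(λ+μ)u)·exp(−kλ(12−u)) du.

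For k = 2 the integral equals 12μ·exp(−24λ)·[exp(12λ−12μ) − 1]/(12λ−12μ).
- 10% stopping: 0.450 + 0.1054 × 0.25 × 0.8/0.5878 = 0.4858.
- 30% stopping: 0.350 + 0.3567 × 0.25 × 0.4/0.3365 = 0.4560.

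| Stopping | k | True 1-year PFS | Excess in Kaplan-Meier (50%) |
|---|---|---|---|
| any | 1 | 50.0% | 0 |
| 10% | 2 | 48.6% | 1.4 points |
| 20% | 2 | 47.1% | 2.9 points |
| 30% | 2 | 45.6% | 4.4 points |
| 20% | 3.57 | 44.5% | 5.5 points |
| 30% | 3.57 | 41.7% | 8.3 points |

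**Other starting points.** With an on-drug median of 11.2 months (borrowed from the medullary thyroid cancer trial), Kaplan-Meier tends to 47.6%, and k = 2 gives an excess of 1.4 to 4.4 points. With an assumed median of 6 months it tends to 25.0%, and k = 2 gives 1.2 to 3.6 points.

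**The case against.** The documents do not contain an express rule that scans stop. Section 5.5 sets a scan interval without tying its end to the last dose, Section 2.2.1 mentions post-treatment contacts, and Section 2.5 separates leaving treatment from leaving the study. The 30 to 37 day visit also covers more than laboratory tests and examination: Table 5-1 marks performance status, ECG, symptom inventory, adverse events and an undefined follow-up item. All of this stands. The stop is read from the blank cells in Table 5-1 and from Section 5.3, so the defect is an omission plus passages that do not agree.

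A reader might infer that follow-up ends at the last dose and that these patients can contribute no later PFS event. That is too strong. Deaths are captured for 30 days, and would count if PFS includes death. A reader might also infer that overall prognosis is not observed at all. The term is undefined, overall survival is not an endpoint, and progression on treatment and early deaths are seen, so truncated is the accurate word.

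Finally, nothing in the documents shows that stopping is related to prognosis. The 3.57 multiplier compares drug with placebo in another tumor, at 140 mg daily where this trial starts at 60 mg. It is not a hazard after stopping drug. Even its worst case is well inside the 21-point sampling half-width. These points limit the size of the problem. They do not supply the missing follow-up.

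**Conclusion.** The point holds as an under-specified follow-up plan that does not support its first secondary endpoint. Followed as written, the schedule loses later progression, and most later deaths, for patients who stop without progression.

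The consequence for Kaplan-Meier 1-year PFS is conditional. If the hazard does not change after stopping there is no bias. If it doubles, and 10 to 30% stop, the estimate is about 1.4 to 4.4 points too high at 50%. At the illustrative 3.57 multiplier it is up to 8.3 points. Constant hazards and all three inputs are assumptions. A reader might go further and call the censoring informative; the documents allow that it may be, but do not show it.

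The primary endpoint, best response, is assessed on treatment and is essentially unaffected. The change should be made because it is cheap, but the primary analysis does not depend on it.

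**What to change.** In Section 5.3 and Table 5-1, for patients who stop without progression:
- record routine-care CT or MRI (FDG-PET for bone-only patients), as near as possible to the existing 8-week interval, until progression, death or week 52;
- record the start date of any new anticancer therapy, and keep recording scans after it;
- collect vital status by chart or phone to at least week 52.

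In Section 7, define PFS as progression or death from any cause, count the events found in this way, and add a sensitivity analysis that censors at drug stop or new therapy. Report how many patients stopped without progression. Reconcile Section 2.2.1 with Section 5.3 on contacts, and say in Section 5.5 whether scans continue off drug.

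The cost is amendment wording plus chart review and calls for a few patients at one site. Some scans will fall at irregular times, which blurs progression dates. Nothing here changes treatment. Vital status for all patients beyond week 52 is optional. It would serve objective 7 only, and would mean contacts with every patient.

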5.4 Laboratory Assessments

Laboratory panels are composed of the following:

Hematology					
WBC count with differential (including at minimum: neutrophils, basophils, eosinophils, lymphocytes, monocytes)	hematocritplatelet countRBC counthemoglobin				
• albumin • ALP	creatinineglucose	magnesiumphosphorus			
amylaseALTASTbicarbonateBUN	 ionized calcium or total and corrected calcium lactate dehydrogenase lipase 	potassiumsodiumtotal bilirubintotal protein			
• chloride Urinalysis • appearance	glucose	occult blood			
 color pH specific gravity ketones protein UPCR 	 bilirubin nitrite creatinine urobilinogen 	(microscopic examination of sediment will be performed only if the results of the urinalysis dipstick evaluation are positive)			
 Other TSH, Free T3 and T4 Pregnancy text (urine or serum) for women of child-bearing potential 		 PT/INR or PTT 24 hour urine collection for protein 			

ALP, alkaline phosphatase; ALT, alanine aminotransferase; AST, aspartate aminotransferase; BUN, blood urea nitrogen; ESR, erythrocyte sedimentation rate; GGT, γ -glutamyltransferase; INR, International Normalized Ratio; PT, prothrombin time; PTT partial thromboplastin time; RBC, red blood cell; TSH, thyroid stimulating hormone; UPCR, urine protein/creatinine ratio; WBC, white blood cell.

Abnormalities in clinical laboratory tests that lead to a change in subject management (eg, dose delayed [withheld] or reduced, requirement for additional medication, treatment or monitoring) are considered clinically significant for the purposes of this study, and will

be recorded on the Adverse Events Case Report Form (CRF). If laboratory values constitute part of an event that meets criteria defining it as serious, the event (and associated laboratory values) must be reported as an SAE.

5.5 Tumor Measurements

Tumor response should be assessed at a frequency of 8 weeks for the first 52 weeks (and then every 12 weeks after that) by CT/MRI and based on RECIST 1.1. In patients with bone metastases, an FDG-PET scan will be obtained every 8 weeks for the first 52 weeks (and then every 12 weeks after that). Subjects continuing to show benefit (complete response [CR], partial response [PR], or stable disease [SD]) may continue on study. Subjects with PD should have their treatment discontinued (unless the investigator, with approval of the Medical Monitor, judges the patient is deriving clinical benefit), and they should enter the post-treatment phase of the study. The same method for tumor assessment should be employed at every assessment.

5.6 MDASI

We will use paper or a secure electronic method to collect patient questionnaires when the patient is in the clinic. We will use an interactive voice response (IVR) system, secure web access, or phone calls by field coordinators when patients are away from the clinic. The method of collecting the patient questionnaire assessments will be based on patient preference and may be varied throughout the study based on patient request.

Data collection by IVR. IVR systems are programmed to call patients at home for symptom assessment. The IVR system asks patients to rate each symptom and interference item on the MDASI-Pheo/PGL 0–10 numeric scales using the keypad of a touchtone telephone. Participants electing to use the IVR system may be provided with an informational brochure outlining the steps to complete an IVR call (Appendix G). A telephone number will be provided in the event of questions or problems. Patients will also be given a Patient Identification Number (PIN) for access to the system. IVR calls will be scheduled at a time that is convenient for the patient. Completion or failure of calls will be monitored by the research staff. In the event of missed calls, a notification screen will appear in the IVR system to alert the research staff. The research staff will then contact the patient by telephone, check on their status and, if possible, complete the assessment with the patient during the telephone interview. With the patient's approval, the system then will continue calling the patient at the preset schedule. The IVR symptom and interference data will be available on an MD Anderson intranet site with access

limited to authorized project staff only. Patient data will be identified by subject study number.

Data collection by secure web access. Study questionnaires may be collected and managed using REDCap (Research Electronic Data Capture) electronic data capture tools hosted at MD Anderson. REDCap (www.project-redcap.org) is a secure, web-based application with controlled access designed to support data capture for research studies, providing: 1) an intuitive interface for validated data entry; 2) audit trails for tracking data manipulation and export procedures; 3) automated export procedures for seamless downloads to common statistical packages; and 4) procedures for importing data from external sources. In the case of multi-center studies REDCap uses Data Access Groups (DAGs) to ensure that personnel at each institution are blinded to the data from other institutions. REDCap (https://redcap.mdanderson.org) is hosted on a secure server by MD Anderson Cancer Center's Department of Research Information Systems & Technology Services. REDCap has undergone a Governance Risk & Compliance Assessment (05/14/14) by MD Anderson's Information Security Office and was found to be compliant with Health Insurance Portability and Accountability Act (HIPAA), Texas Administrative Codes 202-203, University of Texas Policy 165, federal regulations outlined in 21CFR Part 11, and MD Anderson Institutional Policy #ADM0335. Those having access to the data file include the study PI and research team personnel. Users are authenticated against MD Anderson's Active Directory system. External collaborators are given access to projects once approved by the project sponsor. The application is accessed through Secure Socket Layer (SSL). All protected health information (PHI) will be removed from the data when it is exported from REDCap for analysis. All dates for a given patient will be shifted by a randomly generated number between 0 and 364, thus preserving the distance between dates. Dates for each patient will be shifted by a different randomly generated number. Following publication, study data will be archived in REDCap.

Completion or failure of electronic questionnaire completion will be monitored by the research staff. In the event of missed assessments, the research staff will then contact the patient by telephone, check on their status and, if possible, complete the assessment with the patient during the telephone interview. With the patient's approval, the system then will continue sending email requests for questionnaire completion to the patient at the preset schedule.

6 SAFETY

6.1 Adverse Events and Laboratory Abnormalities

6.1.1 Adverse Events

An AE is any untoward medical occurrence in a patient or clinical investigation subject who has been enrolled in a clinical study and who may have been given an investigational product, regardless of whether or not the event is assessed as related to the study treatment. An AE can therefore be any unfavorable and unintended sign (including an abnormal laboratory finding), symptom, or disease temporally associated with the use of an investigational product, regardless of whether or not the event is assessed as related to the investigational product. Pre-existing medical conditions that worsen during a study should be recorded as AEs. Abnormal laboratory values, ECG findings, or vital signs are to be recorded as AEs if they meet the criteria described in Section 3.3.

All untoward events that occur after start of study drug through 30 after the decision to discontinue study treatment (or the date the subject is deemed to be a screen failure) are to be recorded by the investigational site. This requirement includes AEs from unscheduled as well as scheduled visits.

Adverse events will be documented in the patient's official medical record and in the patient's essential source document. All grades will be recorded in the electronic database (CORe), and the attribution of Not-Related and Related will be assessed. Assessment of the relationship of the AR to the study treatment by the investigator is based on the following two definitions:

- Not Related: A not-related AE is defined as an AE that is not associated with the study treatment and is attributable to another cause or there is no evidence to support a causal relationship;
- Related: A related AE is defined as an AE where a causal relationship between the event and the study treatment is a reasonable possibility. A reasonable causal relationship is meant to convey that there are facts (eg, evidence such as dechallenge/rechallenge) or other clinical arguments to suggest a causal relationship between the AE and study treatment.

6.1.2 Serious Adverse Events

The SAE definition and reporting requirements are in accordance with the International Conference of Harmonisation (ICH) Guideline for Clinical Safety Data Management: Definitions and Standards for Expedited Reporting, Topic E2A.

Serious Adverse Event Reporting (SAE) for M. D. Anderson-sponsored IND Protocols:

An adverse event or suspected adverse reaction is considered "serious" if, in the view of either the investigator or the sponsor, it results in any of the following outcomes:

- Death
- A life-threatening adverse drug experience any adverse experience that places the patient, in the view of the initial reporter, at immediate risk of death from the adverse experience as it occurred. It does not include an adverse experience that, had it occurred in a more severe form, might have caused death.
- Inpatient hospitalization or prolongation of existing hospitalization
- A persistent or significant incapacity or substantial disruption of the ability to conduct normal life functions.
- A congenital anomaly/birth defect.

Important medical events that may not result in death, be life-threatening, or require hospitalization may be considered a serious adverse drug experience when, based upon appropriate medical judgment, they may jeopardize the patient or subject and may require medical or surgical intervention to prevent one of the outcomes listed in this definition. Examples of such medical events include allergic bronchospasm requiring intensive treatment in an emergency room or at home, blood dyscrasias or convulsions that do not result in inpatient hospitalization, or the development of drug dependency or drug abuse (21 CFR 312.32).

- Important medical events as defined above, may also be considered serious adverse events. Any important medical event can and should be reported as an SAE if deemed appropriate by the Principal Investigator or the IND Sponsor, IND Office.
- All events occurring during the conduct of a protocol and meeting the definition of a SAE must be reported to the IRB in accordance with the timeframes and procedures outlined in "The University of Texas M. D. Anderson Cancer Center Institutional Review Board Policy for Investigators on Reporting Unanticipated Adverse Events for Drugs and Devices". Unless stated otherwise in the protocol, all SAEs, expected or unexpected, must be reported to the IND Office, regardless of attribution (within 5 working days of knowledge of the event).
- All life-threatening or fatal events, that are unexpected, and related to the study drug, must have a written report submitted within 24 hours (next working day) of knowledge of the event to the Safety Project Manager in the IND Office.
- Unless otherwise noted, the electronic SAE application (eSAE) will be utilized for safety reporting to the IND Office and MDACC IRB.
- Serious adverse events will be captured from the time of the first protocol-specific intervention, until 30 days after the last dose of drug, unless the participant withdraws consent. Serious adverse events must be followed until clinical recovery is complete and laboratory tests have returned to baseline, progression of the event has stabilized, or there has been acceptable resolution of the event.

Additionally, any serious adverse events that occur after the 30 day time period that are related to the study treatment must be reported to the IND Office. This may include the development of a secondary malignancy.

Reporting to FDA:

 Serious adverse events will be forwarded to FDA by the IND Sponsor (Safety Project Manager IND Office) according to 21 CFR 312.32.

It is the responsibility of the PI and the research team to ensure serious adverse events are reported according to the Code of Federal Regulations, Good Clinical Practices, the protocol guidelines, the sponsor's guidelines, and Institutional Review Board policy.

